 - o mean peripartum change in haemoglobin and haematocrit as well as haemoglobin drop > 2 g/dL,
 - o transfer to intensive care unit (ICU),
 - o or death from any cause.
- To assess potential adverse effects of TXA:
 - o Hemodynamic parameters,
 - o adverse gastrointestinal events, renal, hepatic, and coagulation function,
 - o and any venous or arterial thrombosis at any time during the woman's postoperative course.

METHODOLOGY

Research design

Open-label parallel randomized control trial.

Target population

Women undergoing caesarean sections at Sally Mugabe and Parirenyatwa Hospitals based on set inclusion and exclusion criteria.

Inclusion criteria

- Estimated gestational age of 37 weeks or more
- Live intrauterine foetus
- Elective or emergency caesarean delivery
- Signed informed consent

Exclusion criteria including any of the following factors or conditions identified prior to surgery

- History of coagulopathies or conditions predisposing them to thromboembolic phenomena,
- seizure history,
- autoimmune disease,
- placental abruption,
- placenta praevia,
- abnormally adherent placentae if identified on prenatal ultrasound,
- eclampsia or HELLP syndrome,
- known hypersensitivity to TXA,
- planned general anaesthesia,
- caesarean delivery for the second twin or second/third triplet(s) after vaginal birth of the first twin,
- poor understanding of English/Shona languages,
- those who have received anticoagulants in the week before delivery
- persons-under-investigation for COVID-19 and confirmed COVID-19 positive women.

Women will receive individual information in late pregnancy about the trial from obstetricians and midwives during antenatal clinic visits or from anaesthetists during the pre-caesarean visit, or both. Women may be pre-included (receive information and sign consent forms) for caesareans both before and during labour when the investigator considers that the woman is likely to have a caesarean delivery. The aim of pre-inclusion is to facilitate recruitment, particularly the recruitment of caesareans during labour, which may be decided upon and performed in emergency situations. Women recruited prior to emergency caesarean delivery (in labour) sign consent to have the caesarean section while in labour. We therefore consider that having received information about the trial during the antenatal period and on the labour ward, they will also be able to provide informed consent for inclusion into the trial at the same time.

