Study Setting

The study will be performed at two tertiary institutions that are affiliated to the University of Zimbabwe that serve as referral centres for clinics located in Harare as well as district and provincial hospitals in the surrounding provinces: Sally Mugabe Central Hospital Maternity Unit and Parirenyatwa Group of Hospitals i.e. Mbuya Nehanda Maternity Hospital (MNMH). Most of these patients understand both English and Shona languages.

Sample size

The sample size has been calculated assuming a proportion of 2.1% PPH in the experimental group and 5.8% (34) in the control group at 95% confidence interval and 90% power using the Fleiss formula giving a minimum sample size of

$$n = \frac{\left[\frac{Z_{\alpha}\sqrt{(r+1)\overline{p}\overline{q}} + Z_{\beta}\sqrt{rp_{1}q_{1} + p_{2}q_{2}}\right]^{2}}{r(p_{1} - p_{2})^{2}}$$

$$n = \frac{\left[\frac{1.96\sqrt{(1+1) \times 0.0395 \times 0.9605} + 1.28\sqrt{0.021 \times 0.979 + 0.058 \times 0.942}\right]^{2}}{(0.021 - 0.058)^{2}}$$

= 581 per group

Thus, total minimum sample size N = 1, 162 women

Where: n = sample size

 Z_{α} = 1.96 at 95% confidence interval

```
\alpha = probability of a type I error (significance level) = 0.05 \beta = probability of a type II error (1 – power of test)
```

 p_1 = proportion of PPH in the experimental group = 0.021

 p_2 = proportion of PPH in the control group = 0.058

r = ratio of control group/population 2 to experimental group/population 1

q = 1-p

Randomization

A randomized allocation to study and control groups using computer-generated random numbers will be prepared by the trial statistician.

Pharmacy Plan

Oxytocin iv is dispensed weekly from the pharmacy to theatre, where it is stored in a refrigerator in the custody of the sister in charge. All patients undergoing caesarean delivery routinely receive 10IU oxytocin iv, administered slowly by the anaesthetist after delivery of baby at Sally Mugabe Hospital Maternity Unit and Mbuya Nehanda Maternity Hospital. Cold chain will be maintained up to the administration of drug to the patient.

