Preoperative haematocrit will be determined on the day before elective caesarean or on the day of emergency caesarean delivery. Postoperative haematocrit will be the haematocrit obtained by blood sampling at D2 (on the second morning after caesarean section). If haematocrit is not available at D2, then haematocrit at D3 will be considered; if it is also missing, then the postpartum haematocrit closest to D2 in the absence of transfusion will be considered (36,37).

All women who receive RBC transfusion for PPH between delivery and D2 postpartum are defined to have PPH and meet the criteria for the primary outcome. Calculated blood loss is impossible to determine for these women. Moreover, women only rarely receive an RBC transfusion for a blood loss less than 1000 ml. As a marker of significant maternal morbidity, RBC transfusion is considered equivalent or superior to blood loss greater than 1000 mL(25).

Although visual estimation is the method used frequently by anaesthetists to estimate blood loss, it has been demonstrated as inaccurate in repeated studies. The estimate of blood loss is affected by amniotic fluid as well. Its continued use in clinical practice is likely related to tradition and it being easily used. We will also take note of the visual estimate made by the anaesthetist, and by the operating surgeon, as this is the method used locally(6,38)(39)

Secondary outcome measures

Describing postpartum blood loss

1. Clinical

- a. Visually estimated blood loss
- b. proportion of women requiring supplementary uterotonic treatment
- c. incidence of postpartum transfusion
- d. mean number of RBC units transfused
- e. incidence of emergency surgery for PPH including caesarean hysterectomies
- f. incidence of hypovolemic shock related to PPH as determined by assessing BP and pulse
- g. incidence of transfer to ICU
- h. incidence of maternal death from any cause
- i. length of hospital stay.

2. Laboratory

- a. incidence of calculated blood loss > 500 mL and > 1500 mL
- b. mean total calculated blood loss
- c. mean peripartum change in haemoglobin (difference between haemoglobin before delivery and at D2)
- d. Haemoglobin drop > 2 g/dL (between haemoglobin before delivery and at D2) (34).

Describing adverse events

1. Clinical

a. Hemodynamic parameters (heart rate, blood pressure) 15, 30, 45, 60, and 120 min after delivery

- b. the occurrence of potential mild adverse effects of TXA in the operating room:
 - i. nausea
 - ii. vomiting

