 - iii. sensation of rings or spots of light in visual field
 - iv. dizziness
- c. the occurrence of potential severe adverse effects of TXA during the hospital stay and up to discharge
 - i. deep vein thrombosis, if the diagnosis is confirmed by Doppler ultrasound
 - ii. pulmonary embolism, if the diagnosis is confirmed by radiological examination
 - iii. myocardial infarction
 - iv. seizure
 - v. renal failure requiring dialysis
- d. any other unexpected adverse events

Data Management

The researcher and assistants will allocate each patient codes. No identifiers will be used. Any data collected will be stored in an office accessible only to the researcher and research assistants, as well as on a password-protected laptop computer.

data cleaning and entry

Completed questionnaires will be checked for validity, accuracy and completeness by the principal investigator before data entry into the computer.

Statistical methods and data reporting

Data analysis and reporting will be guided by the Consolidated Standards of Reporting Trials (CONSORT) and will be done by the researchers with the assistance of the statistician. (34).

The women's demographic characteristics and standard risk factors for PPH will be compared between the two groups.

The main analysis of the primary and secondary outcomes will be performed in the modified intention-to-treat (ITT) population, defined as women who undergo randomization and have a caesarean delivery (except if they withdraw consent or are deemed ineligible after randomization).

We will also analyse two separate per-protocol populations: women from the modified ITT population receiving a uterotonic and TXA (as specified in the protocol) (per-protocol group 1); the other will include women from the modified ITT population receiving a uterotonic and then tranexamic acid or no TXA in the 10min after delivery (per-protocol group 2; for a situation more consistent with routine clinical practice). The baseline characteristics of the trial participants, the management of the third stage of labour, and protocol adherence will be compared by descriptive statistics.

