Quantitative variables will be expressed, as appropriate, as means with standard deviations (and compared by Student's t-test) or as medians with interquartile ranges (compared by the Wilcoxon rank-sum test). Chi-square or Fisher's exact tests will be used, as appropriate, to compare categorical variables. The effects of TXA will be expressed as relative risks with 95% confidence intervals for categorical outcomes and as mean differences with 95% confidence intervals for quantitative outcomes. The results will also be expressed as absolute risk differences with 95% confidence intervals for binary outcomes.

Two specified subgroup analyses will examine the primary outcome in subgroups of women at high risk of PPH. The subgroups will include women who undergo a caesarean during labour and those who are at risk for PPH according to a composite definition (having at least one risk factor with an odds ratio of 3 or greater in the literature (34) history of any of PPH, hypertensive disorder of pregnancy, multiple pregnancy, or caesarean during labour). Moreover, prespecified subgroup analyses will examine the secondary outcomes in the subgroup of women who undergo a caesarean during labour. We will use the Benjamini–Hochberg procedure to adjust for multiple comparisons of secondary outcomes or subgroups (34). A statistical test may be significant by chance but in reality, not significant. The Benjamini-Hochberg method is used to control for this false discovery rate in statistical tests. Statistical analysis will be conducted using Stata v16. Feasibility

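### The Benjamini-Hochberg rule for secondary outcomes also covers the adverse-effect outcomes, so it can label a real moderate harm non-significant

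*Combined protocol and SAP*

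**What the plan says.** The protocol classes adverse effects as secondary outcomes in two places. Under *Secondary Outcomes*, the second main bullet reads "To assess potential adverse effects of TXA". Under *Secondary outcome measures* there are two parts, one on postpartum blood loss and one headed "Describing adverse events". The second part includes "Hemodynamic parameters (heart rate, blood pressure) 15, 30, 45, 60, and 120 min after delivery", four mild effects in the operating room, and "the occurrence of potential severe adverse effects of TXA during the hospital stay and up to discharge", with five named events.

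*Statistical methods and data reporting* then applies the Benjamini-Hochberg "procedure to adjust for multiple comparisons of secondary outcomes or subgroups". It does not say which comparisons form the family, how many there are, what false discovery rate is used, or whether efficacy and safety are pooled. It makes no exception for safety. The same section adds that "prespecified subgroup analyses will examine the secondary outcomes in the subgroup of women who undergo a caesarean during labour", which repeats the comparisons in a subset.

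Effects are to be given as relative risks, mean differences and risk differences with 95% confidence intervals. No adjustment of those intervals is mentioned.

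**The concern.** Determining adverse effects is one of the trial's two objectives. The plan explains its use of Benjamini-Hochberg as protection against results that are significant only by chance. That suits efficacy claims. For harms of a drug proposed for routine prophylaxis, a missed signal is usually the costlier error, and adjustment makes a miss more likely.

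Pooling adds a second problem. The procedure is step-up, so the threshold for any one outcome depends on how many others have small p-values. In a pooled family, identical counts of vomiting could be flagged or not according to whether unrelated blood-loss measures differ between arms.

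**Working it through.** **Inputs from the documents.** 581 women per arm; "probability of a type I error (significance level) = 0.05", two-sided (z = 1.96). Thromboembolism background: 4 events among 2,345 caesarean deliveries, from a meta-analysis described in the literature review.

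**Assumptions.** Benjamini-Hochberg rate q = 0.05; independent tests; illustrative harm rates, because the documents give none for the common adverse effects.

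**The plan's own figure.** The Fleiss formula with 2.1% versus 5.8% gives 579.8 with the printed z values (1.96 and 1.28) and 580.3 with unrounded ones. Rounded up, the latter is 581 per arm, with 90.0% power. The stated sample size reproduces.

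**Family size m.** From *Secondary outcome measures*:
- Blood loss: 9 clinical items plus 5 laboratory items (counting the two blood-loss cut-offs separately) = 14.
- Adverse effects: 4 mild + 5 severe = 9, plus haemodynamics. Heart rate and blood pressure, each measured "15, 30, 45, 60, and 120 min after delivery", make 2 × 5 = 10 comparisons, or 1 if counted as a single item.
- Total: m = 14 + 9 + 1 = 24, or 14 + 9 + 10 = 33.
- If the labour-subgroup repeats and the two primary-outcome subgroups join the same family, m = 2 × 33 + 2 = 68.

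The strictest Benjamini-Hochberg threshold is q/m: 0.05/24 = 0.0021, 0.05/33 = 0.0015, 0.05/68 = 0.0007.

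**Power for a common harm.** Power = Φ{[|p₁ − p₀|√n − z√(2p̄(1 − p̄))] / √(p₀(1 − p₀) + p₁(1 − p₁))}.

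For 10% versus 15%, p̄ = 0.125 and n = 581:
- at 0.05: (1.205 − 1.960 × 0.468)/0.466 = 0.62, power 73%;
- at 0.05/33 (z = 3.17): (1.205 − 3.17 × 0.468)/0.466 = −0.60, power 28%.

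| Assumed harm (control vs TXA) | Unadjusted 0.05 | 0.05/24 | 0.05/33 |
|---|---|---|---|
| 5% vs 10% | 90% | 56% | 53% |
| 10% vs 15% | 73% | 31% | 28% |
| 20% vs 30% | 98% | 81% | 78% |

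**Full step-up procedure, 10% versus 15%.** The table uses only the strictest threshold. Simulating the whole procedure, with each true efficacy effect given a mean z of 3, yields:

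| m | No other true effect | Five true efficacy effects |
|---|---|---|
| 24 | 32% | 49% |
| 33 | 29% | 44% |
| 68 | 22% | 33% |

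At m = 33, the difference between 29% and 44% is the dependence of the safety verdict on blood loss. A separate family of the 19 adverse-effect tests would remove that dependence but leave power at only 34% when no other effect is real.

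**Rare severe events.** Against 0 control events, Fisher's exact test first reaches 0.05 at 6 TXA events (p = 0.031). If nothing else is significant, 10 events are needed at 0.05/24 (p = 0.0019) and 11 at 0.05/33 (p = 0.0009). The background rate is 4/2,345 = 0.17%, and 581 × 0.0017 is about 1 event per arm. A doubling from about that level (0.2% versus 0.4%) has about 1% power unadjusted and effectively none adjusted. A much larger rare harm, 0.5% versus 2.0%, falls from 56% to 12–14%.

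**The case against.** A reader might infer that the plan will generally hide true harms. The documents do not support that, for these reasons.

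- **Large common harms survive.** 20% versus 30% keeps about 78–81% power at the strictest threshold, and 5% versus 10% is still found slightly more often than not.
- **Realistic severe harms are missed anyway.** At the documents' thromboembolism rate the limit is the sample size. Removing the adjustment does not cure it.
- **The lowest figures assume every other test is null.** The meta-analyses cited in the protocol report effects on several blood-loss measures. With ten true efficacy effects, power for 10% versus 15% rises to 53% (m = 33) or 58% (m = 24).
- **A pooled family of 33 is only one reading.** The plan does not say that efficacy and safety are pooled, and it lists them under separate subheadings. Repeated haemodynamic readings and overlapping blood-loss measures are also correlated, which the simulation ignores.
- **Other safeguards remain.** The 95% intervals carry no stated adjustment, adverse events go to the ethics board, the DSMB reviews safety data at intervals, and the stopping provisions set no significance threshold.

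All of this stands, and it limits the claim. It does not justify adjusting the harms. Safety monitoring does not govern how the final report labels an adverse effect. An interval that excludes no effect, printed beside an adjusted non-significant result, is a conflict the plan leaves open.

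**Conclusion.** The concern holds in a limited form. Following the plan as written, the adverse-effect outcomes fall under Benjamini-Hochberg, and this can label a real moderate harm non-significant. For 10% versus 15%, power falls from 73% to 29–32% with no other true effect, or to 44–49% with five true efficacy effects. The loss is smaller for large common harms and immaterial for rare events near the documents' background rate, where there is almost no power to lose. If efficacy and safety are pooled, the safety verdict also depends on the blood-loss results.

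These figures rest on assumed harm rates, q = 0.05, independent tests and a family of 24 to 33. The primary analysis is unaffected. This is a cheap improvement to the analysis wording.

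**What to change.** Amend the multiplicity sentence in *Statistical methods and data reporting* before the data are analysed:

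- Apply Benjamini-Hochberg only to the blood-loss secondary outcomes and the efficacy subgroup analyses. List the comparisons in that family and state the false discovery rate.
- Report adverse-effect outcomes, overall and in the labour subgroup, as counts by arm with unadjusted relative risks and risk differences (mean differences for heart rate and blood pressure) and 95% confidence intervals. Attach no multiplicity-adjusted significance label.

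This needs no new data, visits or participants. The price is more false safety alarms, so the report should ask readers to weigh each nominal difference against the event counts. The low power for rare severe events remains and should be stated as a limitation.
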